5.2.7 Management of diarrhea

Appearance of grade 1-2 diarrhea attributed to study drug toxicity may be treated with supportive care such as loperamide, initiated at the earliest onset (for example 4 mg orally followed by 2 mg orally every 2 hours until resolution of diarrhea).

5.2.8 Management of hyperlipidemia and hyperglycemia

Severity	Everolimus Dose Adjustment and Management Recommendations
Grade 1	No dose adjustment required. Initiate appropriate medical therapy and monitor.
Grade 2	No dose adjustment required. Manage with appropriate medical therapy and monitor.
Grade 3	Temporary dose interruption. Re-initiate everolimus at lower dose. Manage with appropriate medical therapy and monitor.
Grade 4	Discontinue everolimus and treat with appropriate medical therapy.

Treatment of hyperlipidemia should take into account the pre-treatment status and dietary habits of the patient. Grade 2 or higher hypercholesterolemia (>300 mg/dL or 7.75 mmol/L) or grade 2 hypertriglyceridemia or higher (>2.5x upper normal limit) should be treated with a 3-hydroxy-3-methyl-glutaryl (HMG)-CoA reductase inhibitor (e.g. atorvastatin, pravastatin, fluvastatin) or appropriate triglyceride-lowering medication, in addition to diet.

Note: Concomitant therapy with fibrates and an HMG-CoA reductase inhibitor is associated with an increased risk of a rare but serious skeletal muscle toxicity manifested by rhabdomyolysis, markedly elevated creatine phosphokinase (CPK) levels and myoglobinuria, acute renal failure and sometimes death. The risk versus benefit of using this therapy should be determined for individual patients based on their risk of cardiovascular complications of hyperlipidemia.

Dyslipidemia (including hypercholesterolemia and hypertriglyceridemia) has been reported in patients taking everolimus. Monitoring of blood cholesterol and triglycerides prior to the start of everolimus therapy and periodically thereafter as well as management with appropriate medical therapy is recommended.

Hyperglycemia has been reported in patients taking everolimus. Monitoring of fasting serum glucose is recommended prior to the start of everolimus and periodically thereafter. More frequent monitoring is recommended when everolimus is co-administered with other drugs that may induce hyperglycemia. Optimal glycemic control should be achieved before starting a patient on everolimus.

5.2.9 Management of non-infectious pneumonitis

Non-infectious pneumonitis is a class effect of rapamycin derivatives. Cases of non-infectious pneumonitis (including interstitial lung disease) have also been described in patients taking everolimus. Some of these have been severe and on rare occasions, a fatal outcome was observed.

- A diagnosis of non-infectious pneumonitis should be considered in patients presenting with non-specific respiratory signs and symptoms such as hypoxia, pleural effusion, cough or dyspnea, and in whom infectious, neoplastic and other non-medicinal causes have been excluded by means of appropriate investigations. Opportunistic infections such as PJP should be ruled out in the differential diagnosis of non-infectious pneumonitis. Patients should be advised to report promptly any new or worsening respiratory symptoms.

Patients who develop radiological changes suggestive of non-infectious pneumonitis and have few or no symptoms may continue everolimus therapy without dose alteration.

If symptoms are moderate (grade 2), consideration should be given to interruption of therapy until symptoms improve. The use of corticosteroids may be indicated. Everolimus may be reintroduced at a daily dose approximately 50% lower than the dose previously administered.

For cases of grade 3 non-infectious pneumonitis, interrupt everolimus until resolution to less than or equal to grade 1. Everolimus may be re-initiated at a daily dose approximately 50% lower than the dose previously administered depending on the individual clinical circumstances. If toxicity recurs at grade 3, consider discontinuation of everolimus. For cases of grade 4 non-infectious pneumonitis, everolimus therapy should be discontinued. Corticosteroids may be indicated until clinical symptoms resolve.

For patients who require use of corticosteroids for treatment of non-infectious pneumonitis, prophylaxis for pneumocystis jirovecii pneumonia (PJP) may be considered. The two compounds studied most extensively for prophylaxis against PJP have been trimethoprim-sulfamethoxazole, given orally, and pentamidine, given as an aerosol.

If non-infectious pneumonitis develops, the guidelines in the table below should be followed. Consultation with a pulmonologist is recommended for any case of pneumonitis that develops during the study.

Management of non-infectious pneumonitis

Worst grade pneumonitis	Suggested investigations	Management of pneumonitis	Everolimus dose adjustment
Grade 1 (Asymptomatic, radiographic findings only)	CT scans with lung windows.	No specific therapy is required	No dose adjustment required. Initiate appropriate monitoring.
Grade 2 (Symptomatic, not interfering with Activities of Daily Living)	CT scan with lung windows. Consider pulmonary function testing includes: spirometry, DLCO, and room air O ₂ saturation at rest. Consider a bronchoscopy with biopsy and/or BAL. Monitoring at each visit until return to ≤ grade 1. Return to initial monitoring frequency if no recurrence.	Symptomatic only. Consider corticosteroids and/or other supportive therapy if symptoms are troublesome.	Rule out infection and consider interruption of Everolimus until symptoms improve to Grade ≤ 1. Re-initiate Everolimus at one dose level lower. Discontinue Everolimus if failure to recover within ≤ 28 days.
Grade 3 (Symptomatic, Interfering with Daily Living. O ₂ indicated)	CT scan with lung windows and pulmonary function testing includes: spirometry, DLCO, and room air O ₂ saturation at rest. Monitoring at each visit until return to ≤ grade 1. Return to initial monitoring frequency if no recurrence. Bronchoscopy with biopsy and/or BAL is recommended.	Consider corticosteroids if infective origin is ruled out. Taper as medically indicated.	Rule out infection and interrupt Everolimus until symptoms improve to Grade ≤ 1. Consider re-initiating Everolimus at one dose level lower (approximately 50% lower than the dose previously administered depending on individual clinical circumstances) Discontinue Everolimus if failure to recover within ≤ 28 days. If toxicity recurs at Grade 3, consider discontinuation
Grade 4 (Life-threatening, ventilatory support indicated)	CT scan with lung windows and required pulmonary function testing, if possible, includes: spirometry, DLCO, and room air O ₂ saturation at rest. Monitoring at each visit until return to ≤ grade 1. Return to initial monitoring frequency if no recurrence. Bronchoscopy with biopsy and/or BAL is recommended if possible.	Consider corticosteroids if infective origin is ruled out. Taper as medically indicated.	Rule out infection and discontinue Everolimus.

5.2.10 Management of hepatitis reactivation / flare

Reactivation of Hepatitis B (HBV) has been observed in patients with cancer receiving chemotherapy (Yeo 2004). Sporadic cases of Hepatitis B reactivation have also been seen in this setting with everolimus. Use of antivirals during anti-cancer therapy has been shown to reduce the risk of Hepatitis B virus reactivation and associated morbidity and mortality (Loomba 2008). A detailed assessment of Hepatitis B/C medical history and risk factors must be done for all patients at screening, with testing performed prior to the first dose of everolimus.

Monitoring and prophylactic treatment for hepatitis B reactivation

The table below provides detail of monitoring and prophylactic therapy according to the screening results of viral load and serologic markers testing.

Action to be taken based on screening hepatitis B results

Test	Result	Result	Result	Result	Result
HBV-DNA	+	+ or -	-	-	-
HBsAg	+ or -	+	-	-	-
HBsAb	+ or -	+ or -	+ and no prior HBV vaccination	+ or -	- or + with prior HBV vaccination
HBcAb	+ or -	+ or -	+ or -	+	-
Recommendation	Prophylaxis treatment should be started 1-2 weeks prior to first dose of Everolimus Monitor HBV-DNA approximately every 4-8 weeks		No prophylaxis Monitor HBV-DNA approximately every 3-4 weeks		No specific action

Antiviral prophylaxis therapy should continue for at least 4 weeks after last dose of everolimus. For HBV reactivation definition and management guidelines, see the table below.

Guidelines for the management of hepatitis B reactivation

HBV reactivation (with or without clinical signs and symptoms)*


For patients with baseline results: Positive HBV-DNA OR positive HBsAg ----- reactivation is defined as: [Increase of 1 log in HBV-DNA relative to baseline HBV-DNA value OR new appearance of measurable HBV-DNA]
	
Treat: Start a second antiviral medication AND Interrupt Everolimus administration until resolution:
 
 • \leq baseline HBV-DNA levels 
If resolution occurs within \leq 28 days, Everolimus should be re-started at one dose lower, if available. If the patient is already receiving the lowest dose of Everolimus according to the protocol, the patient should restart at the same dose after resolution. Both antiviral therapies should continue at least 4 weeks after last dose of Everolimus. If resolution occurs $>$ 28 days Patients should discontinue Everolimus but continue both antiviral therapies at least 4 weeks after last dose of Everolimus.

For patients with baseline results: Negative HBV-DNA and HBsAg AND [Positive HBsAb (with no prior history of vaccination against HBV), OR positive HBcAb] ----- Reactivation is defined as: New appearance of measurable HBV-DNA
	
Treat : Start first antiviral medication AND Interrupt Everolimus administration until resolution:
 
 • \leq undetectable (negative) HBV-DNA levels 
If resolution occurs within \leq 28 days, Everolimus should be re-started at one dose lower, if available. If the patient is already receiving the lowest dose of Everolimus according to the protocol, the patient should restart at the same dose after resolution. Antiviral therapy should continue at least 4 weeks after last dose of Everolimus. If resolution occurs $>$ 28 days Patients should discontinue Everolimus but continue antiviral therapy at least 4 weeks after last dose of Everolimus.

* All reactivations of HBV are to be recorded as grade 3 (e.g. CTCAE Version 3.0 - Investigations/Other: Viral Reactivation), unless considered life threatening by the investigator, in which case they should be recorded as grade 4. Date of viral reactivation is the date on which the rise or reappearance of HBV-DNA was recorded.

Monitoring for hepatitis C flare

The following two categories of patients should be monitored every 4–8 weeks for HCV flare:

- Patients with detectable HCV RNA-PCR test at screening.
- Patients known to have a history of HCV infection, despite a negative viral load test at screening (including those that were treated and are considered ‘cured’)

For definitions of HCV flare and actions to be taken in the event of a flare, please refer to the table below.

Guidelines for the management of hepatitis C flare

Baseline results	HCV flare definition*	HCV flare management
Detectable HCV-RNA	> 2 log ₁₀ IU/mL increase in HCV-RNA AND ALT elevation > 5 x ULN or 3 x baseline level, whichever is higher.	Discontinue everolimus
Knowledge of past hepatitis C infection with no detectable HCV-RNA	New appearance of detectable HCV-RNA AND ALT elevation > 5 x ULN or 3 x baseline level, whichever is higher.	Discontinue everolimus

* All flares of HCV are to be recorded as grade 3 (e.g. CTCAE Version 3.0 - Investigations - Other: Viral Flare), unless considered life threatening by the investigator; in which case they should be recorded as grade 4. Date of viral flare is the date on which both the clinical criteria described above were met. (e.g., for a patient whose HCV-RNA increased by 2 logs on 01 JAN 2011 and whose ALT reached > 5 x ULN on 22 JAN 2011, the date of viral flare is 22 JAN 2011).

5.3 Concomitant Medications

Patients must be instructed not to take any medications (over-the-counter or other products) during the protocol treatment period without prior consultation with the investigator. The investigator should instruct the patient to notify the study site about any new medications he/she takes after the start of study drug. All medications (other than study drug) and significant non-drug therapies (including physical therapy and blood transfusions) taken within 28 days of starting study treatment through the 30-day safety follow up visit should be reported on the CRF.

5.3.1 Cytochrome P450 and P-glycoprotein inhibitors/inducers/substrates

Co-administration with strong inhibitors of CYP3A4 or PgP should be avoided; and may cause increased everolimus concentrations. For a current table of Substrates, Inhibitors and Inducers please access the following website:
<http://www.fda.gov/Drugs/DevelopmentApprovalProcess/DevelopmentResources/DrugInteractionsLabeling/ucm093664.htm>

Everolimus is metabolized by CYP3A4 in the liver and to some extent in the intestinal wall.

Therefore, the following are recommended:

- Co-administration with strong inhibitors of CYP3A4 (e.g., ketoconazole, itraconazole, ritonavir) or P-glycoprotein (PgP) inhibitor should be avoided.
- Co-administration with moderate CYP3A4 inhibitors (e.g., erythromycin, fluconazole) or PgP inhibitors should be used with caution. If a patient requires co-administration of moderate CYP3A4 inhibitors or PgP inhibitors, reduce the dose of everolimus by approximately 50%. Additional dose reductions to every other day may be required to manage toxicities. If the inhibitor is discontinued, the everolimus dose should be returned to the dose used prior to initiation of the moderate CYP3A4/PgP inhibitor after a washout period of 2 to 3 days.
- **TSC with SEGA:** Everolimus trough concentrations should be assessed approximately 2 weeks after the addition of a moderate CYP3A4/PgP inhibitor. If the inhibitor is discontinued the everolimus dose should be returned to the dose used prior to initiation of the inhibitor and the everolimus trough concentration should be re-assessed approximately 2 weeks later.
- Grapefruit, Seville oranges, and starfruit affect P450 and PgP activity. Concomitant use should be avoided.
- If patients require co-administration of a strong CYP3A4 inducer, consider doubling the daily dose of everolimus (based on pharmacokinetic data), using increments of 5 mg or less. This dose of everolimus is predicted to adjust the AUC to the range observed without inducers. However, there are no clinical data with this dose adjustment in patients receiving strong CYP3A4 inducers. If the strong inducer is discontinued, consider a washout period of at least 3 to 5 days (reasonable time for significant enzyme de-induction), before the everolimus dose is returned to the dose used prior to initiation of the strong CYP3A4 inducer.
- **TSC with SEGA** Patients receiving concomitant strong CYP3A4 inducers (e.g., the enzyme inducing antiepileptic drugs carbamazepine, phenobarbital, and phenytoin) may require an increased everolimus dose to attain trough concentrations of 3 to 15 ng/mL. Double the daily dose of everolimus and assess tolerability. Assess the everolimus trough level two weeks after doubling the dose. Further adjust the dose if necessary to maintain the trough within the 3 to 15 ng/mL range. If the strong inducer is discontinued, the everolimus dose should be returned to the dose used prior to initiation of the strong CYP3A4 inducer and the everolimus trough concentrations should be assessed approximately 2 weeks later.
- This dose adjustment of everolimus is intended to achieve similar AUC to the range observed without inducers. However, there are no clinical data with this dose adjustment in patients receiving strong CYP3A4 inducers. If

the strong inducer is discontinued the everolimus dose should be returned to the dose used prior to initiation of the strong CYP3A4/PgP inducer.

Please refer to the tables below listing relevant inducers and inhibitors of CYP3A and relevant substrates, inducers, and inhibitors of PgP.

5.3.2 Everolimus and drugs influencing CYP3A4 enzyme

Everolimus is a substrate of CYP3A4, and a substrate and moderate inhibitor of the multidrug efflux pump, PgP (PgP, MDR1, and ABCB1). Therefore, extent of absorption and subsequent elimination of systemically absorbed everolimus may be influenced by products that are substrates, inhibitors, or inducers of CYP3A4 and/or PgP. Concurrent treatment with strong CYP3A4-inhibitors should be avoided. Refer to Table 6-2 in section 6 for a comprehensive list of inducers and inhibitors of CYP3A4 and Table 6-3]for a list of relevant substrates, inducers and inhibitors of PgP. Inhibitors of PgP may decrease the efflux of everolimus from brain or tumor and therefore increase everolimus concentrations in these tissues. In vitro studies showed that everolimus is a competitive inhibitor of CYP3A4 and of CYP2D6, potentially increasing the concentrations of products eliminated by these enzymes. Thus, caution should be exercised when co-administering everolimus with CYP3A4 and CYP2D6 substrates with a narrow therapeutic index. Clinical studies have been conducted in healthy subjects to assess pharmacokinetic drug interactions between everolimus and potential CYP3A modifiers (ketoconazole, verapamil, erythromycin, rifampin, midazolam, and HMGCoA reductase inhibitors (statins). Please refer to <http://medicine.iupui.edu/clinpharm/ddis/main-table/> and the tables below.

Clinically relevant drug interactions: inducers, and inhibitors of isoenzyme CYP3A

Inducers

Strong inducers:

avasimibe, carbamazepine, mitotane, phenobarbital, phenytoin, rifabutin, rifampin (rifampicin), St. John's wort (*hypericum perforatum*)

Moderate inducers:

bosentan, efavirenz, etravirine, genistein, modafinil, nafcillin, ritonavir, [talviraline], thioridazine, tipranavir

Weak inducers:

amprenavir, aprepitant, armodafinil (R-modafinil), bexarotene, clobazam, danshen, dexamethasone, Echinacea, garlic (*allium sativum*), ginkgo (*ginkgo biloba*), glycyrrhizin, methylprednisolone, nevirapine, oxcarbazepine, pioglitazone, prednisone, [pleconaril], primidone, raltegravir, rufinamide, sorafenib, telaprevir, terbinafine, topiramate, [troglitazone], vinblastine

Inhibitors

Strong inhibitors:

boceprevir, clarithromycin, cobicistat, conivaptan, elvitegravir, indinavir, itraconazole, ketoconazole, lopinavir, mibefradil, nefazodone, nelfinavir, posaconazole (Krishna et al 2009), ritonavir, saquinavir, telaprevir, telithromycin, tipranavir, troleandamycin, voriconazole

Moderate inhibitors:

Amprenavir, aprepitant, atazanavir, casopitant, cimetidine, ciprofloxacin, cyclosporine, darunavir, diltiazem, dronedarone, erythromycin, fluconazole, fosamprenavir, grapefruit juice (citrus parasidi fruit juice), imatinib, schisandra sphenanthera, tofisopam, verapamil

Clinically relevant drug interactions: substrates, inducers, inhibitors of Pgp and Pgp/CYP3A dual inhibitors

Substrates

colchicine, digoxin, fexofenadine, indinavir, paclitaxel, talinolol, topotecan, vincristine, everolimus

Inducers

rifampin, St John's wort

Pgp Inhibitors and Pgp/CYP3A Dual Inhibitors

amiodarone, azithromycin, captopril, carvedilol, clarithromycin, conivaptan, diltiazem, dronedarone, elacridar, erythromycin, felodipine, fexofenadine, fluvoxamine, ginkgo (ginkgo biloba), indinavir, itraconazole, lopinavir, mibefradil, milk thistle (silybum marianum), nelfinavir, nifedipine, nitrendipine, paroxetine, quercetin, quinidine, ranolazine, rifampin, ritonavir, saquinavir, Schisandra chinensis, St John's wort (hypericum perforatum), talinolol, Telaprevir, telmisartan, ticagrelor, tipranavir, tolvaptan, valsopodar, verapamil

Reference: Internal Clinical Pharmacology Drug-drug interaction (DDI) memo, updated Oct. 2, 2011,29-Oct-2012 which summarizes DDI data from three sources including the FDA's "Guidance for Industry, Drug Interaction Studies", the University of Washington's Drug Interaction Database, and Indiana University School of Medicine's Drug Interaction Table.

5.3.3 Vaccinations

Immunosuppressants may affect the response to vaccination and vaccination during treatment with everolimus may therefore be less effective. The use of live vaccines should be avoided during treatment with everolimus. For pediatric patients with SEGA that do not require immediate treatment, complete the recommended childhood series of live virus vaccinations prior to the start of therapy according to local treatment guidelines. Examples of live vaccines are: intranasal influenza, measles, mumps, rubella, oral polio, BCG, yellow fever, varicella, and TY21a typhoid vaccines.

5.4 Women of Childbearing Potential

Women of childbearing potential (defined as women with regular menses, women with amenorrhea, women with irregular cycles, women using a contraceptive method that precludes withdrawal bleeding, and women who have had a tubal ligation) are required to have a negative serum pregnancy test within 14 days prior to the first dose of everolimus.

Female and male patients (along with their female partners) are required to use highly effective contraception during participation in the study and for 8 weeks following the last dose of everolimus. Highly effective contraception methods include a combination of any two of the following:

- Use of oral, injected, or implanted hormonal methods of contraception
- Placement of an intrauterine device (IUD) or intrauterine system (IUS)
- Barrier methods such as condom or occlusive cap (diaphragm or cervical/vault cap) with spermicidal foam/gel/film/cream/vaginal suppository
- Total abstinence
- Male/female sterilization

If a patient is suspected to be pregnant, everolimus should be immediately discontinued. In addition a positive urine test must be confirmed by a serum pregnancy test. If it is confirmed that the patient is not pregnant, the patient may resume dosing.

If a female patient or female partner of a male patient becomes pregnant during therapy or within 8 weeks after the last dose of everolimus, the investigator must be notified in order to facilitate outcome follow-up.

5.5 Duration of Therapy

If at any time the constraints of this protocol are considered to be detrimental to the patient's health and/or the patient no longer wishes to continue protocol therapy, the protocol therapy should be discontinued and the reason(s) for discontinuation documented in the case report forms.

In the absence of treatment delays due to adverse events, treatment may continue indefinitely until one of the following criteria applies:

- Documented and confirmed disease progression
- Death
- Adverse event(s) that, in the judgment of the investigator, may cause severe or permanent harm or which rule out continuation of study drug
- General or specific changes in the patient's condition render the patient unacceptable for further treatment in the judgment of the investigator
- Suspected pregnancy
- Serious noncompliance with the study protocol
- Lost to follow-up
- Patient withdraws consent
- Investigator removes the patient from study
- The Siteman Cancer Center decides to close the study

Patients who prematurely discontinue treatment for any reason will be followed as indicated in the study calendar.

5.6 Duration of Follow-up

Patients will be followed for 30 days after the last dose of everolimus or until death, whichever occurs first. Patients removed from study for unacceptable adverse events will be followed until resolution or stabilization of the adverse event.

6.0 DOSE DELAYS/DOSE MODIFICATIONS

For patients who do not tolerate the protocol-specified dosing schedule, dose adjustments are permitted in order to allow the patient to continue the study treatment. Details of study treatment schedule adjustments and dose levels are provided below.

Dose level	Dose and schedule
0 (starting dose)	10 mg QD
-1	5 mg QD
-2	2.5 mg QD

If a patient has already decreased 2 dose levels, no further dose reduction is permitted. Patients who need an additional dose reduction will be required to discontinue everolimus.

Please refer to Section 5.3.1 for alternative dose modifications relating to concomitant medications.

The tables below list the dosing guidelines for everolimus-related non-hematologic and hematologic toxicities.

Management of severe or intolerable adverse drug reactions (ADRs) may require temporary dose interruption (with or without dose reduction) of everolimus therapy. If dose reduction is required, the suggested dose is approximately 50% lower than the daily dose previously administered.

The proceeding sections summarize recommendations for dose interruption, reduction, or discontinuation of everolimus in the management of ADRs. General management recommendations are also provided as applicable. Clinical judgment of the treating physician should guide the management plan of each patient based on individual benefit/risk assessment.

Dosing guidelines for Everolimus-related non-hematologic toxicities

Toxicity	Action
Non-Infectious Pneumonitis	See Section 5.2.9
Reactivation of HBV or HCV flare	See Section 5.2.10
AST or ALT elevation Grade 1 (> ULN - 3.0 x ULN) Grade 2 (> 3.0 - 5.0 x ULN)	Maintain current dose level
AST or ALT elevation Grade 3 (> 5.0 - 20.0 ULN)*	Interrupt everolimus administration until resolution to \leq grade 1 (or \leq grade 2 if baseline values were within the range of grade 2). If resolution occurs \leq 7 days, everolimus should be re-started at the dose level prior to interruption. If resolution takes > 7 days, or if event recurs within 28 days, hold everolimus until recovery to \leq grade 1 or baseline grade / value and reintroduce everolimus at one dose level lower, if available.
AST or ALT elevation Grade 4 (> 20 x ULN)*	Interrupt everolimus administration until resolution to \leq grade 1 (or \leq grade 2 if baseline values were within the range of grade 2). If resolution occurs \leq 7 days, everolimus should be re-started at one dose level lower. If resolution takes > 7 days, discontinue everolimus.
Recurrence of grade 4 AST or ALT elevation after dose reduction or toxicity requiring everolimus interruption for > 28 days	Discontinue everolimus.
Intolerable grade 2 mucositis, or grade 3 AE, except hyperglycemia or hypertriglyceridemia or hypercholesterolemia (see Section 5.2.8)	Interrupt everolimus administration until resolution to \leq grade 1 or baseline grade / value. If resolution occurs within \leq 7 days, everolimus should be re-started at the dose level prior to interruption. If resolution takes > 7 days, or if event recurs within 28 days, hold everolimus until recovery to \leq grade 1 or baseline grade / value and reintroduce everolimus at one dose level lower, if available. Patients will be withdrawn from the study if they fail to recover to \leq grade 1 or baseline grade / value within 28 days.
Any other grade 4	Hold everolimus until recovery to grade \leq 1 or baseline value Reintroduce everolimus at one dose level lower, if available.
Grade 3 or 4 clinical liver failure (asterixis or encephalopathy/coma)	Discontinue everolimus
Recurrence of intolerable grade 2 mucositis or grade 3 event after dose reduction	Reduce dose to the next lower dose level, if available. The lowest possible dose level of everolimus is 2.5 mg daily. Below this level, everolimus must be discontinued. If toxicity recurs at Grade 3, consider discontinuation
Recurrence of grade 4 after dose reduction	Discontinue everolimus
Any non-hematologic toxicity requiring everolimus interruption for > 28 days	Discontinue everolimus

* Should HCV flare be confirmed, the guidelines for flare must take precedence

Dosing guidelines for Everolimus-related hematologic toxicities

Toxicity	Action
Grade 3 thrombocytopenia, neutropenia, or anemia	Interrupt everolimus until resolution to grade ≤ 1 If resolution occurs ≤ 7 days, reintroduce everolimus at the dose level prior to interruption. If resolution occurs > 7 days, or event occurs within 28 days, reintroduce everolimus at one dose level lower, if available.
Grade 4 thrombocytopenia, neutropenia, or anemia	Interrupt everolimus until recovery to grade ≤ 1 . Then reintroduce everolimus at one dose level lower, if available.
Febrile neutropenia	Interrupt everolimus until resolution to grade ≤ 1 (or baseline value) and no fever. Reintroduce everolimus at one dose level lower, if available.*
Recurrence of grade 3 toxicity after dose reduction	Reduce dose to the next lower dose level, if available. The lowest possible dose level of everolimus is 5 mg every other day (2.5 mg daily). Below this level, everolimus must be discontinued.
*Recurrence of grade 4 toxicity (including febrile neutropenia) after dose reduction	Discontinue everolimus
*Any hematologic toxicity requiring Everolimus interruption for > 28 days	Discontinue everolimus

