5.2.6 Management of stomatitis / oral mucositis / mouth ulcers

Severity	Everolimus Dose Adjustment and Management Recommendations
Grade 1 (Minimal symptoms, normal diet)	No dose adjustment required. Manage with non-alcoholic or salt water (0.9%) mouth wash several times a day.
Grade 2 (Symptomatic but can eat and swallow modified diet)	Temporary dose interruption until recovery to grade ≤ 1 . Re-initiate everolimus at the same dose. If stomatitis recurs at grade 2, interrupt dose until recovery to grade ≤ 1 . Re-initiate everolimus at a lower dose. Manage with topical analgesic mouth treatments (e.g. benzocaine, butyl aminobenzoate, tetracaine hydrochloride, menthol or phenol) with or without topical corticosteroids (i.e. triamcinolone oral paste)*.
Grade 3 (Symptomatic and unable to adequately eat or hydrate orally)	Temporary dose interruption until recovery to grade ≤ 1 . Re-initiate everolimus at lower dose. Manage with topical analgesic mouth treatments (i.e. benzocaine, butyl aminobenzoate, tetracaine hydrochloride, menthol or phenol) with or without topical corticosteroids (i.e. triamcinolone oral paste)*
Grade 4 (Symptoms associated with life-threatening consequences)	Discontinue everolimus and treat with appropriate medical therapy.

* using agents containing alcohol, hydrogen peroxide, iodine, and thyme derivatives in management of stomatitis as they may worsen mouth ulcers.

Patients with a clinical history of stomatitis/mucositis/mouth ulcers and those with gastrointestinal morbidity associated with mouth/dental infections, irritation of esophageal mucosa e.g. gastroesophageal reflux disease (GERD) and pre-existing stomatitis/mucositis must be monitored even more closely. Patients should be instructed to report the first onset of buccal mucosa irritation/reddening to their study physician immediately.

Stomatitis/oral mucositis/mouth ulcers due to everolimus should be treated using local supportive care. Please note that investigators in earlier trials have described the oral toxicities associated with everolimus as mouth ulcers, rather than mucositis or stomatitis. If your examination reveals mouth ulcers rather than a more general inflammation of the mouth, please classify the adverse event as such. The suggested paradigm for treatment of stomatitis/oral mucositis/mouth ulcers is as follows:

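### Section 5.2.6 and the Section 6 dose table give different restart rules for grade 3 stomatitis that clears within 7 days and, read literally, for grade 4 stomatitis

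*Combined protocol and SAP*

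**What the plan says.** **Section 5.2.6 (stomatitis table).** Grade 3: interrupt until grade 1 or less, then "Re-initiate everolimus at lower dose. Manage with topical analgesic mouth treatments". The row has no condition on time to recovery. Grade 4, described as "Symptoms associated with life-threatening consequences": "Discontinue everolimus and treat with appropriate medical therapy".

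**Section 6 (non-hematologic table).** One row covers intolerable grade 2 mucositis and every grade 3 event except hyperglycemia, hypertriglyceridemia and hypercholesterolemia. If the event resolves within 7 days, "everolimus should be re-started at the dose level prior to interruption". If it takes longer, or recurs within 28 days, the restart is one level lower. A later row, *Any other grade 4*, holds the drug until recovery to grade 1 or less "or baseline value Reintroduce everolimus at one dose level lower, if available".

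**Links between the two.** The Section 6 table sends the reader to 5.2.9 for pneumonitis, 5.2.10 for hepatitis and, within the grade 3 row, 5.2.8 for metabolic events. It does not refer to 5.2.6 or 5.2.1. Its only precedence statement is a footnote on hepatitis C flare. The introduction to Section 6 adds: "The proceeding sections summarize recommendations for dose interruption, reduction, or discontinuation of everolimus in the management of ADRs" and "Clinical judgment of the treating physician should guide the management plan of each patient based on individual benefit/risk assessment".

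**Related rules.** Section 5.2.1 requires discontinuation for invasive systemic fungal infection. Section 5.2.8 requires it for grade 4 hyperlipidemia or hyperglycemia.

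**The concern.** An investigator who opens one table gets a different instruction from one who opens the other. After grade 3 stomatitis with quick recovery, one patient would resume at half the dose and another at the full dose. After grade 4 stomatitis, one physician could stop permanently and another could rechallenge, each following a row of the protocol. What is at stake is patient safety and uniform dosing in a 12-patient trial.

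**Working it through.** **Inputs.** Section 6 dose levels: 10 mg (start), 5 mg, 2.5 mg daily. Planned enrolment of 12: Section 14.1. The plan gives no figure of its own to reproduce on this point, so the check is a comparison of the rules for a first event at 10 mg.

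| Event | Section 5.2 | Section 6, general rows | Same? |
|---|---|---|---|
| Grade 3 stomatitis, resolved in 7 days or less | lower dose: 5 mg | prior dose: 10 mg | No |
| Grade 3 stomatitis, resolved in more than 7 and up to 28 days | lower dose: 5 mg | one level lower: 5 mg | Yes |
| Grade 4 stomatitis, recovered within 28 days | discontinue | 5 mg, if the residual row applies | No, read literally |
| Grade 4 stomatitis, interruption beyond 28 days | discontinue | discontinue | Yes |
| Invasive systemic fungal infection, grade 3 or 4 | discontinue (5.2.1) | restart after recovery | No, read literally |
| Grade 4 hyperglycemia or hyperlipidemia | discontinue (5.2.8) | 5 mg, if the 5.2.8 pointer covers grade 3 only | Arguable |

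**Is the grade 3 difference real?** Yes. The Section 6 row lists its exceptions and stomatitis is not among them. The same row names mucositis, so Section 6 does not leave oral toxicity to 5.2.6. The difference is confined to recovery within 7 days.

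**Is the grade 4 difference real?** Only if *other* means other than the rows around it. The grade 4 events that the table names itself are AST/ALT elevation and clinical liver failure; stomatitis has no grade 4 row there. If *other* also excludes events with their own rule in Section 5.2, the conflict disappears. The text does not choose between these readings.

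**How often might it arise?** The documents give no grade 4 stomatitis rate. For an assumed rate p per patient, expected cases are 12p and the chance of at least one is 1 − (1 − p)^12:

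- p = 0.25%: 12 × 0.0025 = 0.03 cases; 1 − 0.9975^12 = 3.0%
- p = 0.5%: 12 × 0.005 = 0.06 cases; 1 − 0.995^12 = 5.8%
- p = 1%: 12 × 0.01 = 0.12 cases; 1 − 0.99^12 = 11.4%

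These are chances of the event. Divergent treatment also needs recovery within 28 days and a physician who chooses to rechallenge.

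For grade 3 the documents give no rate split by time to recovery. As context only, Section 1.2 lists stomatitis among grade 3–4 reactions at 2% or more. If the combined rate were exactly 2%, the chance of at least one grade 3–4 case in 12 patients would be 1 − 0.98^12 = 21.5%. That is not a rate for either mismatch.

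**The case against.** The strongest reply is that a specific rule displaces a general one. The dedicated stomatitis table would then govern, and the residual grade 4 row would catch only events with no rule elsewhere. The sentence in Section 6 about proceeding sections supports this: it mentions management recommendations, which are what the 5.2.6 and 5.2.8 tables contain and the Section 6 tables mostly do not. Section 6 also presents its adjustments as permitted rather than required.

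This has weight for grade 4 and is why that part is stated conditionally. It does not settle the matter. The sentence can point backward or forward, and it ranks neither table. Section 6 defers by explicit pointer elsewhere and has none to 5.2.6. Nor does the argument remove the grade 3 difference, where Section 6 names mucositis and lists its exceptions.

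The second reply is that the consequences are bounded, and this stands. Both rules stop dosing at once. Restart requires recovery to grade 1 or less, or to baseline. Interruption beyond 28 days, or a repeat grade 4 event after dose reduction, ends treatment under Section 6 as well. Clinical judgment applies throughout, and Section 5.5 allows stopping for "Adverse event(s) that, in the judgment of the investigator, may cause severe or permanent harm or which rule out continuation of study drug".

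A reader might infer that the protocol directs rechallenge after life-threatening stomatitis. It does not: one row permits that reading, while another section says stop.

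**Conclusion.** The point holds as a minor inconsistency in safety text. The grade 3 mismatch (5 mg against 10 mg after recovery within 7 days) is firm. The grade 4 mismatch (permanent stop against 5 mg) and the fungal infection gap hold on a literal reading of Section 6. The grade 4 metabolic gap is arguable, because the 5.2.8 pointer can be read as covering all grades. The event probabilities rest on assumed rates and serve only to show scale.

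A reader might also infer that the trial's statistical result is at risk. The documents do not support that: the RECIST response endpoint, the enrolment of 12 and the rule of 2 or more responders in Section 14 do not refer to these dosing rows.

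**What to change.** In the Section 6 non-hematologic table:

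1. Add a row for grade 3 or 4 stomatitis/oral mucositis pointing to Section 5.2.6 (grade 3, restart at a lower dose; grade 4, discontinue). Except these events from the restart-dose rule in the grade 3 row and from the residual grade 4 row.
2. Add a row for invasive systemic fungal infection: discontinue, per Section 5.2.1.
3. Extend the 5.2.8 pointer to grade 4 metabolic events.

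Leave unchanged the intolerable grade 2 mucositis rule, the recurrence rows, the limit of two dose reductions and the 28-day discontinuation rule.

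Do not add a blanket sentence that Section 5.2 governs. For infections in general, 5.2.1 only asks the physician to consider interruption or discontinuation. Giving that precedence would make optional the interruption that Section 6 now directs for everolimus-related grade 3 and 4 infections.

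The cost is a wording amendment, loss of the full-dose restart after quickly resolving grade 3 stomatitis, and less freedom to rechallenge after the other events. No extra patients, visits or tests are needed.
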